LY3526318 or matching placebo is planned to be administered in an 8-hour fasting state once daily for 14 days. However, following a review of the food effect data from Part A, all doses may be administered with food.

Participants will return to the CRU for a final visit on Day 23.

Number of Participants:

Part A: Approximately 60 participants will be randomized to achieve 8 evaluable participants per cohort (6 LY3526318:2 placebo), except for the 100-mg cohort that will include 8 evaluable females and 4 evaluable males (females: 6 LY3526318:2 placebo; males: 3 LY3526318:1 placebo) and 100-mg food assessment cohort (Cohort 10) that will include 8 evaluable females and all will receive LY3526318 in an open-label manner.

Part B: Approximately 24 participants will be randomized to achieve 8 evaluable participants per cohort (6 LY3526318:2 placebo).

Additional cohorts of up to 8 participants each may be enrolled in either part of the study. Such additional cohorts may be enrolled in case intermediate or additional dose level(s) need to be studied or additional food effect need to be studied at other than planned dose levels.

Statistical Analysis:

Safety: The primary safety endpoints are the numbers of treatment-emergent serious adverse events and adverse events. Summary statistics for each cohort will be provided by dose level and for all placebo participants combined.

Pharmacokinetic Parameters: Plasma PK parameters for LY3526318 and metabolite(s) of interest will be calculated using noncompartmental methods after single- and multiple-dose administration. Pharmacokinetic parameters will be summarized by dose level using descriptive statistics. Mean and individual plasma concentration versus time curves for LY3526318 will be represented graphically.

2 Schedule of Activities

Table 2-1 Study Schedule Protocol J2D-MC-CVAA: Part A Cohorts 1-6 (SAD)

	S	Treatment/ In CRU				Posttreatment	ED^a
Study Day	≤28	-1	1	2	3	10	
Visit Window (days)						±2	
Visits	1^b	2^c				3	
CRU admission		X					
CRU discharge					X		
Participant information (including I/E criteria)	X	X					
Informed consent	X						
Medical history	X						
Height	X						
Weight	X		X			X	X
Physical examination (complete [C] or directed [D])	C	D	D	D	D	C	C
Urine drug screen and ethanol test	X	X					
Vital signs including temperature	X	X	X (predose, 2 h, 4 h, 8 h)	X	X	X	X
Hematology and clinical chemistry	X	X		X ^d	X ^d	X	X
Urinalysis ^e	X	X					
Pregnancy test (serum beta-hCG) ^f	X	X				X	X

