- ^d All 8 female participants in Cohort 10 will receive LY3526318 in a 3-period crossover with standardized high fat meals administered prior to dose, and at 30 min and 1 hour post dose. Participants receiving meals post dose administration will receive their dose in the fasted state. Periods are separated by a washout period of at least 1 week.

Cohorts administered above LY3526318 100 mg are anticipated to exceed the approximate 10x margin to the projected no-observed-adverse-event-level (NOAEL)-equivalent exposure for males; for this reason, only female participants will be enrolled at dose levels higher than 100 mg. Additionally, if exposure data from previous cohorts does not support dose escalation in males through 100 mg, males will be discontinued from further dosing in the study.

The effect of food on LY3526318 PK will be explored in female participants only, in the 100-mg cohort and in the 400-mg cohort. In the 100-mg cohort, the initial dose will be administered after an approximately 8-hour fast in 8 female and 4 male participants, followed by a washout period of at least 1 week. A second dose will be administered after a standardized high-fat meal in female participants only. In the 400-mg cohort, the initial dose will be administered after an approximately 8-hour fast; following a washout period of at least 1 week, the second dose will be administered after a standardized high-fat meal. Except for the food effect assessment cohorts, all other doses are to be administered after an approximately 8-hour fast. Following a review of the 100-mg and/or 400-mg fed and fasted data, subsequent cohorts may be administered with food.

An additional cohort (Cohort 10) will assess the effect of food on LY3526318 PK in 8 female participants. All participants in this cohort will receive 100 mg LY3526318 with standardized high fat meal in an open-label, 3-way crossover manner (meal administered prior to dose, at 30 minutes and at 1 hour post dose; [Table 2-2](#)). Participants receiving meals post dose administration will receive their dose after an approximately 8-hour fast. Periods will be separated by a washout period of at least 1 week.

All participants will return to the CRU for a final visit approximately 9 days after study drug administration or after the fed-state dose for female participants in 100- and 400-mg cohorts.

Part B (MAD):

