7.4.1.1 Part A

Dose escalation from the 10-mg cohort to the 50-mg cohort may occur after review of safety data from at least 6 participants in the 10-mg cohort. The subsequent dose escalations may occur after review of safety and available PK data through 48 hours postdose from at least 6 participants in the prior cohort. The second dose of the 100-mg cohort, food effect assessment, may occur after review of safety and available PK data from the first 3 days of fasted dose in at least 6 participants in Cohort 4 (400-mg dose). The second dose of the 400-mg cohort, in the fed state, may occur after review of Cohort 6 (1000-mg dose) safety and available PK data for at least 6 participants through 48 hours postdose.

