3.0 Introduction

This Statistical Analysis Plan (SAP) describes the statistical methods that will be used during the analysis and reporting of data collected under Eli Lilly and Company Protocol J2D-MC-CVAA.

This SAP should be read in conjunction with the study protocol and electronic case report form (eCRF). This version of the plan has been developed using the protocol dated 16-Dec-2019 (including all amendments up to this protocol date) and the final eCRFs (see [Table 1](#)).

Table 1 eCRF versions

Cohort	Date
Cohorts 1, 2, 3, 4 (Period 1), and 4	12-Jul-2019
Cohorts 4 (Period 2) and 6	07-Oct-2019
Cohorts 7, 8, and 9	04-Nov-2019
Cohort 10	22-Jan-2020

An approved and signed SAP is a requirement for database lock. An approved SAP is also required for unblinding of the study treatments.

This SAP only covers the results that will be processed by the PRA Early Development Services (EDS) Biostatistics Department.

PRA EDS will perform evaluation of:

- pharmacokinetic (PK) data,
- safety and tolerability data.

This SAP supersedes the statistical considerations identified in the protocol; where considerations are substantially different, they will be so identified. Any post-hoc or unplanned analyses, or significant changes from the planned analysis in this SAP performed to provide results for inclusion in the clinical study report (CSR) but not included in this SAP, will be clearly identified in Section 9.8.2 of the CSR. Changes to planned analyses do not require an updated SAP but should be included in the CSR if significant.

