6.0 Study Design

This is a Phase 1 single-center, randomized, double-blind, placebo-controlled, single ascending dose (SAD, Part A) and multiple ascending dose (MAD, Part B) study of LY3526318 in healthy participants.

Part A - SAD

The single-ascending doses of LY3526318 or placebo will be administered, at planned dose levels of 10, 50, 100, 400, 800, and 1000 mg, in 6 cohorts of 8 participants each, except the 100-mg cohort that will include 12 participants. The dose levels may change subject to available safety and PK data review.

Participants in the first cohort (10 mg, Cohort 1) will not be stratified by sex. A fixed number of females and males will be randomized in Cohorts 2 and 3 and the participants will be stratified to ensure equal distribution between females and males. Cohorts administered above LY3526318 100 mg are anticipated to exceed the approximate 10x margin to the projected no-observed-adverse-event-level (NOAEL)-equivalent exposure for males; for this reason, only female participants will be enrolled at dose levels higher than 100 mg. Randomization to LY3526318 or placebo will be 3:1 within each cohort or stratum, respectively.

Following a screening period of up to 28 days, eligible participants will be confined to the clinical research unit (CRU) from Day -1 until all study assessments are completed on Day 3. A sentinel dosing strategy will be utilized for the first dose level (Cohort 1, 10 mg). Two participants will receive a sentinel dose (1 each with LY3526318 and placebo) and the remaining participants will be administered after review of safety data up to 48 hours postdose. Dose escalation from the 10-mg to 50-mg cohort may occur after review of safety data from at least 6 participants in the 10-mg cohort. Dose escalations to subsequent cohorts may occur after review of safety data and available PK data through 48 hours postdose from at least 6 participants in the prior cohort.

The effect of food on LY3526318 PK will be explored in female participants only in Cohort 3 and in Cohort 4. The initial dose will be administered after an approximately 8-hour fast, followed by a washout period of at least 1 week, a second dose will be administered after a standardized high-fat meal.

Except for the food effect assessment cohorts, all other doses are to be administered after an approximately 8-hour fast. Following a review of the 100-mg and/or 400-mg fed and fasted data, subsequent cohorts may be administered with food.

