18.1.1 Adverse Events

Treatment-emergent adverse events (TEAE) are those which occur after the first dose of study drug.

All AEs (including non-treatment-emergent events) will be listed, including the AE description (verbatim term), Medical Dictionary for Regulatory Activities (MedDRA) system organ class (SOC) and preferred term (PT), start date and time, end date and time, severity, relation to study drug, seriousness, action taken, and outcome.

All AE summaries will include only TEAE. All TEAEs occurring following dosing will be attributed to the treatment that was received.

A breakdown of the number of TEAEs, and the number and percentage of subjects reporting each TEAE, categorized by system organ class and preferred term coded according to MedDRA (Version 22.1), will be presented by treatment and overall for each study part. One table is presented for all TEAEs and one table is presented for TEAEs considered to be related to the study medication. Subjects will only be counted once within each SOC or PT per treatment.

Additionally, a summary table with TEAEs by severity and relationship to study drug will be presented by study part and treatment.

The following missing data will be imputed as defined (for calculations only / will not be presented):

- Missing AE start and / or end times for the calculation of onset and duration will be assumed to be at 00:01 for a start time and 23:59 for end times
- Missing AE severity or relationship will be assumed to be severe or related, respectively
- Missing AE start times for the determination of treatment emergence will be assumed to occur after treatment unless partial date documents the AE as happening prior to treatment
- Missing AE start times for the determination of treatment assignment will be assumed to occur after treatment on the recorded date
- Missing AE start date will be assumed to be after treatment for the determination of TEAE and on treatment

For the US Clinical Trials Registry (CTR), a CTRAE summary table and the CTRAESUMM SAS dataset will be provided separately from the TFL created for CSR. The table and corresponding dataset will be created according to the specifications provided by the Sponsor.

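### The SAP puts no upper time limit on attributing TEAEs to a dose, so 4 of the 11 active Part A conditions are observed over a window of unknown length and the by-treatment percentages need not be comparable

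*SAP*

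**What the plan says.** The protocol synopsis states that "The primary safety endpoints are the numbers of treatment-emergent serious adverse events and adverse events". SAP 18.1.1 then sets three rules:

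- Definition: "Treatment-emergent adverse events (TEAE) are those which occur after the first dose of study drug". This gives a start and no end.
- Attribution: "All TEAEs occurring following dosing will be attributed to the treatment that was received". For a participant who receives two or three treatments, the rule does not say which one takes the event. The most recent dose is the natural reading, but it is not written down.
- Counting: "Subjects will only be counted once within each SOC or PT per treatment". The tables show the number of events and the number and percentage of participants, by treatment. No person-time is planned.

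For the food-effect cohorts (3 and 4), SAP 6.0 describes a fasted dose "followed by a washout period of at least 1 week, a second dose will be administered after a standardized high-fat meal". No maximum gap is given. Protocol 7.4.1.1 also makes the fed dose wait for other cohorts: Cohort 3 waits for Cohort 4, and for Cohort 4 "The second dose of the 400-mg cohort, in the fed state, may occur after review of Cohort 6 (1000-mg dose") data. Follow-up is tied to the final dose. Protocol 5.1 says "All participants will return to the CRU for a final visit approximately 9 days after study drug administration or after the fed-state dose", and Appendix 5 confirms that the follow-up laboratory sample is taken only after the fed dose. Cohort 10 is similar: its periods are at least 1 week apart with no maximum, and Protocol Table 2-2 gives the Day 10 visit to Period 3 only.

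Under Protocol 9.2.1, SAEs are collected for 30 days after the last dose, and investigators need not actively seek events after a participant has completed the study. SAP 9.1.4 pools placebo within each part and keeps the fed-period placebo separate.

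**The concern.** The table of TEAEs by treatment answers the primary Part A objective, and its natural use is to compare dose columns with each other and with placebo. A percentage of participants with at least one event rises with the length of observation, even when the drug does nothing. AEs are recorded throughout study participation, so background events that a participant has at home between the fasted and fed doses count against the fasted dose. In a single-dose cohort, an event at the same distance from dosing may fall after the participant has completed the study and never be recorded.

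If the gaps are long, the 100 mg and 200 mg fasted columns gain background events, and so does part of the placebo pool. If the gaps are close to 7 days, these columns have slightly less time than the rest. In both cases, with about 6 active participants per column, one or two extra events can look like a dose pattern.

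**Working it through.** **Length of the windows.** The plan's figure of about 9 days reproduces: Day 10 − Day 1 = 9. With the ±2-day visit window the range is 7 to 11 days.

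The minimum inter-period gap is the larger of the 7-day washout and the chain of 48-hour reviews in Protocol 7.4.1.1:

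- Cohort 3: max(7, 2 + 2) = 7 days
- Cohort 4: max(7, 2 + 2 + 2) = 7 days
- Cohort 10: 7 days (washout only)

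No maximum can be derived for any of them.

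**Which conditions are affected.** The SAP Appendix 4 example table has 6 fasted and 5 fed active columns, 11 in all.

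- Open until the next dose (4): 100 mg fasted and 200 mg fasted (Cohorts 3 and 4, Period 1); 100 mg fed −30 min and +30 min (Cohort 10, Periods 1 and 2). SAP 6.2 records that the Cohort 3 males were not dosed, so the whole 100 mg fasted column is a two-period group.
- Closed at 7 to 11 days (7): 10, 30, 50 and 300 mg fasted; 30 mg and 200 mg fed; 100 mg fed +60 min.

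Fasted placebo: 2 participants × 6 cohorts = 12, of whom 4 come from Cohorts 3 and 4.

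**What this does with no drug effect.** The documents give no background AE rate, so I assume a constant 0.1 or 0.2 AE per participant-week. P(w) = 1 − exp(−rate × w/7), with w in days. For a Cohort 3 or 4 fasted column against pooled fasted placebo, let both cohorts have gap w and the other 8 placebo participants 9 days. The spurious difference is P(w) − [8·P(9) + 4·P(w)]/12 = (2/3)·[P(w) − P(9)].

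| Window w | P(w), 0.1/week | Expected of 6 | Difference from placebo | P(w), 0.2/week | Difference from placebo |
|---|---|---|---|---|---|
| 7 days | 9.5% | 0.6 | −1.7 points | 18% | −3.0 points |
| 9 days | 12% | 0.7 | 0 | 23% | 0 |
| 28 days | 33% | 2.0 | +13.9 points | 55% | +21.6 points |
| 42 days | 45% | 2.7 | +22.0 points | 70% | +31.5 points |

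Example for 28 days at 0.1: P(28) = 1 − exp(−0.4) = 0.330; P(9) = 1 − exp(−0.129) = 0.121; (2/3)(0.330 − 0.121) = 0.139.

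The sign changes at about 9 days. For SAEs the comparison differs, because final doses are followed for 30 days: an open condition has the shorter SAE window whenever its gap is below 30 days.

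**With a common 7-day window.** Under the same model every column has the same expected percentage (9.5% at 0.1 per week), and the spurious difference is 0.

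**The case against.** The strongest reply is that the consequence is limited. The study is not powered on a hypothesis, SAP 9.4.3 plans no formal testing, and AE summaries are descriptive. The SAP also has a table of related TEAEs and one by severity and relationship, and the report's in-text AE tables (11.3 and 11.4 in SAP Appendix 3) are the related-TEAE tables. Most at-home events judged unrelated would not reach those. Each AE is listed with its start date and time, and dosing is listed too, so a late event can be traced.

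All of this is correct and lowers the priority. It does not remove the point: the primary endpoint is all TEAEs, and a listing does not give the reader a comparable percentage.

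Three stronger readings are tempting, and the documents do not support them:

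- *The mid-dose fasted columns will be inflated.* The only gap length that the documents fix is the 7-day minimum, at which the effect is small and reversed. The escalation gates make longer gaps plausible, but they were written for the planned doses. SAP 6.2 shows that Cohorts 4, 5 and 6 received 200, 300 and 30 mg, so whether those gates set the actual timing cannot be established.
- *The eCRF dates show a gap of about 12 weeks in Cohort 4.* SAP Table 1 dates the form for "Cohorts 4 (Period 2) and 6" 87 days after the form covering Cohort 4 Period 1. These are form versions. The earlier one also serves Cohorts 1 to 3, which were dosed before Cohort 4. The dates say nothing reliable about a dosing interval and should not be used as evidence of one.
- *Only Cohorts 3 and 4 are affected, and every other dose has about 9 days.* Cohort 10 Periods 1 and 2 have the same open gap, and about 9 days describes routine AE follow-up, not SAEs.

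**Conclusion.** The point holds in a limited form, as a cheap improvement. The attribution rule has no end, and 4 of 11 active conditions plus about 4 of 12 fasted placebo participants have windows set by an uncapped gap. By-treatment TEAE percentages are therefore not comparable when the gaps differ from about 9 days. Neither the size nor the direction of the bias is known: over gaps of 7 to 42 days and 0.1 to 0.2 AE per week, the spurious difference from pooled fasted placebo runs from −3 to about +31 points. The rates and all gaps above 7 days are assumptions, as are the constant rate and equal gaps in Cohorts 3 and 4. No type I error or power is involved.

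**What to change.** In SAP 18.1.1, before database lock and unblinding:

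1. State that each TEAE is assigned to the most recent dose before its onset.
2. Keep the all-TEAE table as planned.
3. Add a Part A by-treatment table restricted to dosing through 7 days post-dose, and use it to compare dose levels with placebo. Seven days is the longest window that the schedule lets every condition complete: it is both the minimum washout and the earliest follow-up (Day 8). A cut-off at Day 12 would not equalise the windows, because the visit may fall anywhere from Day 8 to Day 12 and the next dose may come 7 days after the last.
4. Show events after 7 days in a separate row under the same treatment.
5. Report participant-days at risk for every treatment column, including the Cohort 10 conditions and pooled placebo. This also covers early discontinuations.

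The cost is one extra table and a window flag in ADAE. Late-onset events fall outside the restricted comparison, but remain in the all-TEAE table and in the separate row.

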9.2.1 Serious Adverse Events

An SAE is any AE from this study that results in 1 of the following:

- death
- initial or prolonged inpatient hospitalization
- a life-threatening experience (i.e. immediate risk of dying)
- persistent or significant disability/incapacity
- congenital anomaly/birth defect
- important medical events that may not be immediately life threatening or result in death or hospitalization but may jeopardize the patient or may require intervention to prevent 1 of the other outcomes listed in the definition above.

The CRU personnel must alert the Lilly medical monitor, or its designee, of any SAE as soon as practically possible.

Additionally, CRU personnel must alert Lilly Global Patient Safety, or its designee, of any SAE within 24 hours of investigator awareness of the event via a sponsor-approved method. If alerts are issued via telephone, they are to be immediately followed up with official notification on study-specific SAE forms. This 24-hour notification requirement refers to the initial SAE information and all follow-up SAE information.

Although all AEs are recorded in the case report form or EDC after signing informed consent, SAE reporting to the sponsor begins after the participant has signed informed consent and has received the study drug. However, if an SAE occurs after signing informed consent, but prior to receiving the study drug, AND is considered reasonably possibly related to a study procedure then it MUST be reported.

Investigators are not obligated to actively seek AEs or SAEs in participants once they have discontinued from and/or completed the study. Serious adverse events will be collected for 30 days after the last dose of study drug. However, if the investigator learns of any SAE, including a death, at any time after a participant has been discharged from the study, and he/she considers the event reasonably possibly related to the study drug or study participation, the investigator must promptly notify Lilly within 24 hours.

Pregnancy (maternal or paternal exposure to the study drug) does not meet the definition of an AE. However, to fulfill regulatory requirements any pregnancy should be reported following the SAE process to collect data on the outcome for both mother and fetus.

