Appendix 2: Schedule of Assessments

Study Schedule Protocol J2D-MC-CVAA: Part A Cohorts 1-6 (SAD)

	S	Treatment/ In CRU			Posttreatment		ED ^a
Study Day	≤28	-1	1	2	3	10	
Visit Window (days)						±2	
Visits	1 ^b		2 ^c			3	
CRU admission		X					
CRU discharge					X		
Participant information (including I/E criteria)	X	X					
Informed consent	X						
Medical history	X						
Height	X						
Weight	X		X			X	X
Physical examination (complete [C] or directed [D])	C	D	D	D	D	C	C
Urine drug screen and ethanol test	X	X					
Vital signs including temperature	X	X	X (predose, 2 h, 4 h, 8 h)	X	X	X	X
Hematology and clinical chemistry	X	X		X ^d	X ^d	X	X
Urinalysis ^e	X	X					
Pregnancy test (serum beta-hCG) ^f	X	X				X	X
HIV, HCV, HBsAg	X						
ECG ^g	X		X (predose, 2 h, 4 h, 8 h)			X	X
C-SSRS	X	X				X	X
Randomization			X				
Study drug administration ^h			X				
PK blood sample ⁱ			X	X	X		X
PK 24-hour urine collection ^j			↔ X →				
Adverse event				↔ X →			
Concomitant medications				↔ X →			

Abbreviations: C = complete physical examination; CRU = clinical research unit; C-SSRS= Columbia-Suicide

Severity Rating Scale; D = directed physical examination; ECG = electrocardiogram; ED = early discontinuation; h = hour; HBsAg = hepatitis B surface antigen; hCG = human chorionic gonadotropin; HCV = hepatitis C virus; HIV = human immunodeficiency virus; I/E = inclusion/exclusion; PK = pharmacokinetics; S = screening; SAD = single-ascending dose.

^a Participants who discontinue from the study prior to study completion should complete the ED visit procedures.

^b Screening will be performed within 28 days of the first dose being administered.

^c All participants will remain in the CRU until completion of Day 3 procedures.

^d Hematology and clinical chemistry sample to be taken in the morning.

^e A standard urine test strip/dipstick may be used.

^f A serum beta-hCG test will be performed in all female participants, except in female participants with confirmed hysterectomy.

^g A single 12-lead ECG will be recorded in the supine position after 5 minutes of rest.

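### An AE with no start date is always counted as treatment-emergent, even when its recorded end date is before the first dose

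*SAP*

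**What the plan says.** SAP 18.1.1 defines the concept first: "Treatment-emergent adverse events (TEAE) are those which occur after the first dose of study drug". It then lists imputation rules for incomplete AE records. Two of them bear on treatment emergence.

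- For a missing start time, the event is taken as post-treatment, with an exception: "unless partial date documents the AE as happening prior to treatment".
- For a missing start date, the rule is: "Missing AE start date will be assumed to be after treatment for the determination of TEAE and on treatment". No exception follows.

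The same section restricts all AE summaries to TEAEs and sets a missing relationship to related. The AE listing carries "start date and time, end date and time, severity, relation to study drug, seriousness, action taken, and outcome", so the end date is available in the data.

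On what can be in the database before dosing, Protocol 9.2.1 says: "Although all AEs are recorded in the case report form or EDC after signing informed consent". SAP 6.0 gives the length of the pre-dose window for each part: "Following a screening period of up to 28 days". Participants are admitted only on Day -1, so nearly all of that window is spent outside the unit.

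**The concern.** Treating an event of unknown timing as treatment-emergent is a reasonable cautious default. The difficulty is narrower: the rule also covers events whose timing is partly known and known to be pre-dose. A participant may report at admission a complaint from screening that has already cleared, with a date for when it stopped but none for when it began. Applied as written, the rule places that event on treatment.

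AEs and SAEs are the primary endpoints of both parts, and the Protocol synopsis describes them as counts of treatment-emergent events. A wrong flag therefore puts a false event into a dose or placebo column of the primary tables (14.3.1.1 and 14.3.1.3). If the relationship were missing as well, the event would also enter the related-TEAE table (14.3.1.2), which is the AE table reproduced in the text of the report as Tables 11.3 and 11.4.

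**Working it through.** The plan states no figure to reproduce. The check compares the rules and then does simple arithmetic on group sizes.

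**Logic.** Let S be the start date of the event, E its end date and D the date of first dose.

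1. An event cannot end before it starts, so S ≤ E.
2. Suppose S is missing and E is recorded with E < D. Then S ≤ E < D, so S < D for certain.
3. The missing-date rule sets S after treatment. That is impossible given E, and it contradicts the definition of a TEAE in the same section.

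**Does another rule prevent this?**

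| Place | What it does | Does it cover the case? |
|---|---|---|
| SAP 18.1.1, missing start time | Exempts events that a partial date places before treatment | No. It concerns start times, depends on a partial date and does not mention end dates |
| SAP 18.1.1, missing start date | Assumes post-treatment and on treatment | This is the rule at issue |
| SAP 9.1.2 | No imputation unless noted elsewhere | No. It leaves the AE rules in force |
| SAP 14.0 | Classes a medication that ended before first dose as prior | No, medications only. It shows that the plan already uses end-date logic |

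**Size if triggered.** SAP 9.1.3 bases percentages on participants exposed within a treatment. The change for one misclassified participant is 1/n.

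| Group | n | 1/n |
|---|---|---|
| Active arm of a cohort randomized 6:2 | 6 | 16.7 points |
| Pooled Part B placebo (3 cohorts × 2) | 6 | 16.7 points |
| Pooled fasted Part A placebo (6 cohorts × 2) | 12 | 8.3 points |
| Cohort 10, all active | 8 | 12.5 points |

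The Part A placebo count uses two placebo participants in Cohort 3, because SAP 6.2 says the males were not dosed and that cohort had eight participants. Under SAP 9.1.1, frequency percentages print as integers, so 16.7 appears as 17. With an end-date exception the change is zero in every row, and the event stays in the AE listing.

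**The case against.** The strongest reply is that this will hardly ever happen. The site must know when an event ended and yet record no part of its start date, and nothing in the documents suggests that this occurred. Such a record is also an obvious query: SAP 8.2 sends questionable values to the data manager and follows those that affect the tables to resolution. A sensible programmer might also read the imputation rules as filling gaps, not as overriding a recorded end date. The rule fits a worst-case approach in which missing severity becomes severe and missing relationship becomes related. It also gives the right answer for events after discharge. There is no formal hypothesis testing, escalation and stopping rest on safety review during the study, and the listing would show the end date.

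Most of this stands and limits the weight of the point. Three parts do not dispose of it. A query may not recover a date. Double programming of the AE dataset (SAP 9.2.4.1) gives no protection, because both programmers work from the same rule. And over-counting is cautious only in an active column; in a placebo column it raises the comparator rate. The route into the related-TEAE table needs a third coincidence and should carry little weight. The 1/6 figure is what any single event does to a group of six; it does not show how often the rule misfires.

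**Conclusion.** The concern holds. As written, the missing-start-date rule classes an event with a recorded pre-dose end date as treatment-emergent, against the SAP's own definition, and no other text corrects it. The effect is conditional on such a record existing. The documents give no frequency, and it is expected to be rare. If it occurs, one participant shifts a six-person active group or the pooled Part B placebo group by 16.7 percentage points, and the larger groups by 8.3 to 12.5 points, assuming planned group sizes and that the participant has no other TEAE in the same row of the table. This is a minor drafting gap, worth closing because it touches the primary endpoint and costs almost nothing.

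**What to change.** Add to the missing-start-date rule in SAP 18.1.1: *unless the AE end date (complete or partial) is before the first dose of study drug, in which case the AE is not treatment-emergent*. A partial end date should count only if every date consistent with it is before the first dose. An end date that is missing, ambiguous, or on the day of dosing without a time leaves the present default in place.

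The cost is one clause in the SAP and one condition in the ADAE program. No new data are needed, since the end date is already collected and listed. The change is best made before database lock and unblinding, so that nobody has to decide such a case with treatment known. If lock has passed, check ADAE for records with no start date and a pre-dose end date. If there are any, report the reclassification in the study report as a change from the planned analysis, as SAP 3.0 provides.
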